#### [name]

- Answer choices (select one): All of the time (100%), Nearly all of the time (90%), Most of the time (75%), About half the time (50%), Less than half the time (<50%)

- Scoring
  - Those responding "All of the time" or "Nearly all of the time" are considered to be adherent
  - Those responding "Most of the time" or less are considered to be non-adherent
- "Did you take your full dosage of glibenclamide yesterday "10 (Y/N)
- If YES, application skips to the next question
  - If NO, application prompts promoter to ask patient "Did you take your full dosage of glibenclamide today "  $(Y/N) \rightarrow$  application moves on to the next section with either answer

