# Appendix 4 - Hypoglycemia Protocol

# Protocol for identifying probable hypoglycemic episodes

- Patients who are taking glibenclamide are asked the following questions:
  - "In the last month, have you had episodes of any of the following symptoms":
    - Confusion
    - Trembling
    - Feeling uncoordinated
    - Palpitations
    - Abnormal sweating
    - Abnormal anxiousness
  - Patients reporting episodes of any of these symptoms are asked the following questions and their answers are scored as noted:
    - "Did these symptoms come on gradually or did they start suddenly"
      - Gradually (0)
      - Suddenly (+1)
    - "Did these symptoms occur when you had not eaten for several hours or after strenuous physical activity"
      - Yes (+1)
      - No (0)
    - "Did these symptoms improve after eating something
      - Yes (+1)
      - No (0)
- Patient considered to have probable hypoglycemia if above answers total to 2 or more points

and because the original validation study used this standard as well, we define adherence as taking medication "Nearly all of the time" or "All of the time".

<sup>10 Glibenclamide functions as an insulin secretagogue and has a duration of action of ~24 hours. Thus, it is expected to have a relatively short-term effect on blood glucose and it is essential to know the timing of the last dose when interpreting and acting on a patient's blood glucose level.

<sup>1These symptoms were found to be the most highly correlated with experimentally-induced hypoglycemia.

 <sup>12 In general, the onset of hypoglycemia symptoms is rapid rather than gradual
  This question assesses for the association of symptoms with two common risk factors for hypoglycemia that are likely to be present in our population

[name]

- Patients who have 2 or more points are asked the following question: "When you had these symptoms, were you so confused or sleepy that someone else needed to help you eat or drink something with sugar "
  - If YES, this is considered as an episode of probable severe hypoglycemia
  - If NO, this is considered an episode of probable mild hypoglycemia

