#### 180(200)≤FBG<400 or 300≤PPBG<HI

- 1. Metformin without problems, adherent
  - a. Metformin 850 mg  $\rightarrow$  metformin 1700 mg
  - b. Metformin 1700 mg  $\rightarrow$  metformin 2550 mg
  - c. Metformin 2550 mg → metformin 2550 mg + glibenclamide 2.5 mg
- 2. Metformin without problems, nonadherent  $\rightarrow$  continue current doses
- 3. Metformin with problems, adherent
  - a. Metformin 850 mg, willing to continue → metformin 850 mg + glibenclamide 2.5 mg
  - b. Metformin 850 mg, not willing to continue  $\rightarrow$  glibenclamide 2.5 mg
  - c. Metformin 1700 mg  $\rightarrow$  metformin 850 mg + glibenclamide 2.5 mg
  - d. Metformin 2550 mg  $\rightarrow$  metformin 1700 mg + glibenclamide 2.5 mg
- 4. Metformin with problems, nonadherent  $\rightarrow$  same as #3
- 5. Glibenclamide without problems, no previous problems with metformin, took yesterday
  - a. Glibenclamide 2.5 mg  $\rightarrow$  metformin 1700 mg + glibenclamide 2.5 mg
  - b. Glibenclamide 5 mg  $\rightarrow$  metformin 1700 mg + glibenclamide 5 mg
  - c. Glibenclamide 10 mg  $\rightarrow$  metformin 1700 mg + glibenclamide 10 mg
- 6. Glibenclamide without problems, no previous problems with metformin, did not take yesterday
  - a. Glibenclamide 2.5 mg  $\rightarrow$  metformin 1700 mg
  - b. Glibenclamide 5 mg  $\rightarrow$  metformin 1700 mg + glibenclamide 2.5 mg
  - c. Glibenclamide 10 mg  $\rightarrow$  metformin 1700 mg + glibenclamide 5 mg
[name]

- 7. Glibenclamide without problems, previous problems with metformin, took yesterday
  - a. Agrees to take metformin  $\rightarrow$  metformin 850 mg + current glibenclamide dose
  - b. Refuses to take metformin
    - i. Glibenclamide 2.5 mg  $\rightarrow$  glibenclamide 5 mg
    - ii. Glibenclamide 5 mg  $\rightarrow$  glibenclamide 10 mg
    - iii. Glibenclamide 10 mg  $\rightarrow$  glibenclamide 10 mg
- 8. Glibenclamide without problems, previous problems with metformin, did not take yesterday  $\rightarrow$  same as #7
- 9. Glibenclamide with hypoglycemia symptoms, no previous problems with metformin, took yesterday
  - a. Glibenclamide 2.5 mg  $\rightarrow$  metformin 1700 mg
  - b. Glibenclamide 5 mg  $\rightarrow$  metformin 1700 mg + glibenclamide 2.5 mg
  - c. Glibenclamide 10 mg  $\rightarrow$  metformin 1700 mg + glibenclamide 5 mg
- 10. Glibenclamide with hypoglycemia or hypoglycemia symptoms, no previous problems with metformin, did not take yesterday → same as #9

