- 11. Glibenclamide with hypoglycemia symptoms, previous problems with metformin, took yesterday
  - a. Agrees to take metformin
    - i. Glibenclamide 2.5 mg  $\rightarrow$  metformin 850 mg
    - ii. Glibenclamide 5 mg  $\rightarrow$  metformin 850 mg + glibenclamide 2.5 mg
    - iii. Glibenclamide 10  $mg \rightarrow$  metformin 850 mg + glibenclamide 5 mg
  - b. Refuses to take metformin
    - i. Glibenclamide 2.5 mg  $\rightarrow$  MD consult
    - ii. Glibenclamide 5 mg  $\rightarrow$  glibenclamide 2.5 mg
    - iii. Glibenclamide 10 mg  $\rightarrow$  glibenclamide 5 mg
- Glibenclamide with hypoglycemia symptoms, previous problems with metformin, did not take yesterday → same as #11
- 13. Metformin and glibenclamide without problems, adherent, took glibenclamide yesterday
  - a. Metformin 850 mg + glibenclamide any dose → metformin 1700 mg + glibenclamide current dose
  - b. Metformin 1700 mg + glibenclamide any dose → metformin 2550 mg + glibenclamide current dose
  - c. Metformin 2550 mg + glibenclamide 2.5 mg  $\rightarrow$  metformin 2550 mg + glibenclamide 5 mg
  - d. Metformin 2550 mg + glibenclamide 5-10 mg  $\rightarrow$  metformin 2550 mg + glibenclamide 10 mg
- 14. Metformin and glibenclamide without problems, nonadherent, took glibenclamide yesterday  $\rightarrow$  continue current doses
- 15. Metformin and glibenclamide without problems, adherent, did not take glibenclamide yesterday → continue current doses
- Metformin and glibenclamide without problems, nonadherent, did not take glibenclamide yesterday → continue current doses
- 17. Metformin and glibenclamide, problems with metformin, adherent, took glibenclamide yesterday
  - a. Agrees to take metformin
    - i. Metformin 850 mg + glibenclamide 2.5 mg  $\rightarrow$  metformin 850 mg + glibenclamide 5 mg
  - ii. Metformin 850 mg + glibenclamide 5-10 mg  $\rightarrow$  metformin 850 mg + glibenclamide 10 mg b. Refuses to take metformin
    - i. Metformin 850 mg + glibenclamide 2.5 mg  $\rightarrow$  glibenclamide 5 mg
    - ii. Metformin 850 mg + glibenclamide 5 mg  $\rightarrow$  glibenclamide 10 mg
    - iii. Metformin 850 mg + glibenclamide 10 mg → glibenclamide 10 mg, MD consult
  - c. Metformin 1700 mg + glibenclamide 2.5 mg → metformin 850 mg + glibenclamide 5 mg
  - d. Metformin 1700 mg + glibenclamide 5-10 mg  $\rightarrow$  metformin 850 mg + glibenclamide 10 mg
  - e. Metformin 2550 mg + glibenclamide 2.5 mg  $\rightarrow$  metformin 1700 mg + glibenclamide 5 mg

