#### [name]

f. Metformin 2550 mg + glibenclamide 5-10 mg → metformin 1700 mg + glibenclamide 10 mg

- 18. Metformin and glibenclamide, problems with metformin, nonadherent, took glibenclamide yesterday
  - a. Metformin 850 mg + glibenclamide any dose, agrees to take metformin →metformin 850 mg + current glibenclamide dose
  - Metformin 850 mg + glibenclamide any dose, refuses to take metformin → current glibenclamide dose
  - c. Metformin 1700 mg + glibenclamide any dose  $\rightarrow$  metformin 850 mg + current glibenclamide dose
  - d. Metformin 2550 mg + glibenclamide any dose → metformin 1700 mg + current glibenclamide dose
- Metformin and glibenclamide, problems with metformin, adherent, did not take glibenclamide yesterday → same as #18
- 20. Metformin and glibenclamide, problems with metformin, nonadherent, did not take glibenclamide yesterday → same as #18
- 21. Metformin and glibenclamide, hypoglycemia symptoms, adherent, took glibenclamide yesterday
  - a. Metformin 850 mg + glibenclamide 2.5 mg  $\rightarrow$  metformin 1700 mg
  - b. Metformin 850 mg + glibenclamide 5 mg  $\rightarrow$  metformin 1700 mg + glibenclamide 2.5 mg
  - c. Metformin 850 mg + glibenclamide 10 mg  $\rightarrow$  metformin 1700 mg + glibenclamide 5 mg
  - d. Metformin 1700 mg + glibenclamide 2.5 mg  $\rightarrow$  metformin 2550 mg
  - e. Metformin 1700 mg + glibenclamide 5 mg  $\rightarrow$  metformin 2550 mg + glibenclamide 2.5 mg
  - f. Metformin 1700 mg + glibenclamide 10 mg  $\rightarrow$  metformin 2550 mg + glibenclamide 5 mg
  - g. Metformin 2550 mg + glibenclamide 2.5 mg  $\rightarrow$  metformin 2550 mg
  - h. Metformin 2550 mg + glibenclamide 5 mg  $\rightarrow$  metformin 2550 mg + glibenclamide 2.5 mg
- i. Metformin 2550 mg + glibenclamide 10 mg  $\rightarrow$  metformin 2550 mg + glibenclamide 5 mg
- 22. Metformin and glibenclamide, hypoglycemia symptoms, nonadherent, took glibenclamide yesterday
  - a. Metformin 850 mg + glibenclamide 2.5 mg  $\rightarrow$  metformin 1700 mg
  - b. Metformin 850 mg + glibenclamide 5 mg  $\rightarrow$  metformin 1700 mg + glibenclamide 2.5 mg
  - c. Metformin 850 mg + glibenclamide 10 mg  $\rightarrow$  metformin 1700 mg + glibenclamide 5 mg
  - d. Metformin 1700 mg + glibenclamide 2.5 mg  $\rightarrow$  metformin 1700 mg
  - e. Metformin 1700 mg + glibenclamide 5 mg  $\rightarrow$  metformin 1700 mg + glibenclamide 2.5 mg

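### Appendix 10, highest glucose band: row 8 raises glibenclamide for a metformin refuser who missed yesterday's full dose, while the comparable rows of the band turn the same rise into a hold

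*Combined protocol and SAP*

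**What the plan says.** Appendix 3 has the CHW ask "Did you take your full dosage of glibenclamide yesterday". Footnote 10 gives the reason: glibenclamide acts for about 24 hours, so "it is essential to know the timing of the last dose when interpreting and acting on" a glucose level. Appendix 10 then splits the glibenclamide rows by that answer.

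The relevant rows of the band 180(200)≤FBG<400 or 300≤PPBG<HI are these:

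- **Row 7** (glibenclamide alone, no hypoglycemia symptoms, previous metformin problems, dose taken). Patients who accept metformin get 850 mg plus their current glibenclamide (7a). Refusers go from 2.5 to 5 mg or from 5 to 10 mg, or stay at 10 mg (7b).
- **Row 8**, "Glibenclamide without problems, previous problems with metformin, did not take yesterday": handled exactly as row 7.
- **Row 13**, "Metformin and glibenclamide without problems, adherent, took glibenclamide yesterday": with metformin at 2550 mg, glibenclamide is raised (13c-d).
- **Row 15**, "Metformin and glibenclamide without problems, adherent, did not take glibenclamide yesterday": all doses continue.
- **Row 17**, "Metformin and glibenclamide, problems with metformin, adherent, took glibenclamide yesterday": glibenclamide is raised, including for refusers (17b).
- **Row 19**, "Metformin and glibenclamide, problems with metformin, adherent, did not take glibenclamide yesterday": handled as row 18, which keeps glibenclamide where it is. The refuser line, 18b ("Metformin 850 mg + glibenclamide any dose, refuses to take metformin"), leaves the current dose.

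Section 6.5 allows escalation to 5 and then 10 mg when goals are unmet after at least a month. Section 2.7.2 reserves monthly up-titration for readings well above goal.

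**The concern.** A high reading after a missed dose cannot tell an inadequate dose from an untaken one. Row 8 treats it as inadequate and dispenses twice the milligrams the same day. If the patient then takes the new dose daily, exposure rises for a reason the reading did not establish. Section 2.7.1 regards glibenclamide as probably the most harmful drug used here, and documented hypoglycemia is a primary safety endpoint (section 4.1.3).

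The glibenclamide-only rows of Appendix 10 have no adherent/nonadherent split. Row 8 therefore pools a patient who missed only yesterday with patients who miss often, and yesterday's dose is the only adherence signal those rows carry.

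**Working it through.** The plan gives no figure to reproduce, so this is a comparison of rows.

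**Step 1: how often does yesterday's answer matter in this band?** There are 12 took/did-not-take pairs. The action is identical in 8: 7/8, 9/10, 11/12, 14/16, 18/20, 22/24, 25/27 and 26/28. It differs in 4: 5/6, 13/15, 17/19 and 21/23. Glibenclamide itself differs in 3 of those (5/6, 13/15, 17/19).

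**Step 2: where does the took-yesterday row raise glibenclamide, and what happens after a missed dose?**

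| Took row | Cells that rise | Did-not-take row | After a missed dose |
|---|---|---|---|
| 7b (refuses metformin) | 2.5 and 5 mg: 2 | 8 | 2 rise |
| 13c-d (metformin 2550 mg) | 2.5 and 5 mg: 2 | 15 | 2 hold |
| 17 (four metformin states) | 4 × 2 = 8 | 19, via 18 | 8 hold |
| Total | 2 + 2 + 8 = 12 | | 10 hold, 2 rise |

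The four metformin states in row 17 are 850 mg accepted, 850 mg refused, 1700 mg and 2550 mg.

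**Step 3: the closest comparison.** Among refusers only, 7b and 17b each have 2 rising cells. After a missed dose the 17b cells hold (19b) and the 7b cells still rise (row 8). In 17b metformin is refused, and in 13c-d it is already at its maximum, so there too glibenclamide is the only program drug left to raise. Rows 15 and 19 are for patients rated adherent, which Appendix 3 sets at nearly all the time (90%) or better. The plan thus holds even for a mostly adherent patient who missed yesterday.

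**Step 4: all did-not-take rows.** Of the 6 in this band without hypoglycemia symptoms, row 6 lowers glibenclamide, rows 15, 16, 19 and 20 hold it, and row 8 raises it. The symptomatic did-not-take rows lower it. In the lower bands the row 8 refuser is stopped (FBG <80(90)), lowered or stopped (80(90) to 130(150)), or continued (130(150) to 180(200)). No other did-not-take row in Appendix 10 raises glibenclamide.

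**Step 5: reach.** Assume refusers match the 5% that section 2.7.1 gives for stopping metformin over gastrointestinal effects:

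- Patients: 5% × 100 = 5, to 5% × 150 = 7.5, taken as 8.
- Appendix 10 visits in 6 months: months 1, 2, 4 and 5, so 4 each (months 3 and 6 use Appendix 11). 5 × 4 = 20, to 8 × 4 = 32.
- Share of those visits meeting every other condition: 1% to 20%, assumed and not in the documents. 20 × 1% = 0.2, to 32 × 20% = 6.4.

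That is fewer than 1 to about 6 such increases.

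**The case against.** The best defence is that row 8 follows the plan's own rules. Section 6.5 escalates without any last-dose condition, a reading in this band meets section 2.7.2, and footnote 10 forbids nothing. All of that stands. It also applies word for word to the patients in rows 15 and 19, whom the plan holds, so it permits the rise without explaining the difference.

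A reader might infer that the rest of the band uses yesterday's answer and row 8 alone ignores it. The documents do not support that, since 8 of the 12 pairs give the same action either way. Rows 16 and 20 are weak comparators too: their took-yesterday partners, 14 and 18, also hold, so those holds reflect nonadherence. What stands out in row 8 is the combination of ignoring the answer and raising the dose.

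The count of 10 in 12 should not be leaned on heavily. Eight of the 10 held cells come from one cross-reference (row 19 to row 18), only 2 are refusers, and the other 8 patients remain on metformin as well.

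A missed full dose may be a partial one, and the application goes on to ask about today's dose. However, Appendix 3 moves on whatever the reply, and row 8 makes no use of it.

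Nor do the documents support reading this as a serious unguarded hazard. Symptomatic patients are diverted at the same visit to rows 11 and 12, which lower the dose or, for a refuser on 2.5 mg, send the patient to a physician. Telephone advice is available during the visit, CHWs work alongside a coordinator for the first several months, patients are taught about hypoglycemia, a physician reviews within 1 week, and the dose is capped at 10 mg. Section 2.6 holds that most of the effect comes at 2.5 mg, so twice the milligrams is not twice the effect.

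**Conclusion.** The point holds as an unexplained inconsistency in one row, in the direction of more sulfonylurea. That row 8 raises the dose, and is the only did-not-take row in Appendix 10 to do so, follows directly from the text. The strength of the contrast rests on two comparisons: 13c-d with 15, and above all 17b with 19b.

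The size is small: 2 of row 8's 3 starting doses are affected for refusers, with fewer than 1 to about 6 increases in 6 months under the assumed rates. The 5% describes stopping metformin, not refusal among glibenclamide-only patients, so the range is only an order of magnitude. Appendix 10 also borrows this band's doses for some readings of 400 or above, which widens the row's use slightly.

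A reader might go further and infer a bias in the A1c endpoints. Nothing in the documents supports that, and no effect on the analysis is claimed. Appendix 11 does not ask about yesterday's dose. Above goal with glucose still high, it raises a refuser rated adherent (row 7b) and holds a nonadherent one (row 8b), so it does not settle the matter either way. This is a worthwhile, inexpensive safety correction.

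**What to change.** Replace the cross-reference in row 8 of this band with two lines:

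- 8a, accepts metformin: add metformin 850 mg and leave glibenclamide unchanged (as now).
- 8b, refuses metformin: leave glibenclamide unchanged at 2.5, 5 or 10 mg, with the adherence counselling of section 11.4.

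Update the application and repeat the alpha test for that row. If the medical director does intend the rise, a footnote to row 8 giving the reason would serve instead.

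The cost is one row of text, one application edit and one test, with no extra patients, visits or data. The clinical downside is that a mostly adherent refuser who missed only yesterday's dose waits until the next visit for an increase. The plan already accepts that wait in rows 15 and 19.

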#### [name]

f. Metformin 2550 mg + glibenclamide 5-10 mg → metformin 1700 mg + glibenclamide 10 mg

- 18. Metformin and glibenclamide, problems with metformin, nonadherent, took glibenclamide yesterday
  - a. Metformin 850 mg + glibenclamide any dose, agrees to take metformin →metformin 850 mg + current glibenclamide dose
  - Metformin 850 mg + glibenclamide any dose, refuses to take metformin → current glibenclamide dose
  - c. Metformin 1700 mg + glibenclamide any dose  $\rightarrow$  metformin 850 mg + current glibenclamide dose
  - d. Metformin 2550 mg + glibenclamide any dose → metformin 1700 mg + current glibenclamide dose
- Metformin and glibenclamide, problems with metformin, adherent, did not take glibenclamide yesterday → same as #18
- 20. Metformin and glibenclamide, problems with metformin, nonadherent, did not take glibenclamide yesterday → same as #18
- 21. Metformin and glibenclamide, hypoglycemia symptoms, adherent, took glibenclamide yesterday
  - a. Metformin 850 mg + glibenclamide 2.5 mg  $\rightarrow$  metformin 1700 mg
  - b. Metformin 850 mg + glibenclamide 5 mg  $\rightarrow$  metformin 1700 mg + glibenclamide 2.5 mg
  - c. Metformin 850 mg + glibenclamide 10 mg  $\rightarrow$  metformin 1700 mg + glibenclamide 5 mg
  - d. Metformin 1700 mg + glibenclamide 2.5 mg  $\rightarrow$  metformin 2550 mg
  - e. Metformin 1700 mg + glibenclamide 5 mg  $\rightarrow$  metformin 2550 mg + glibenclamide 2.5 mg
  - f. Metformin 1700 mg + glibenclamide 10 mg  $\rightarrow$  metformin 2550 mg + glibenclamide 5 mg
  - g. Metformin 2550 mg + glibenclamide 2.5 mg  $\rightarrow$  metformin 2550 mg
  - h. Metformin 2550 mg + glibenclamide 5 mg  $\rightarrow$  metformin 2550 mg + glibenclamide 2.5 mg
- i. Metformin 2550 mg + glibenclamide 10 mg  $\rightarrow$  metformin 2550 mg + glibenclamide 5 mg
- 22. Metformin and glibenclamide, hypoglycemia symptoms, nonadherent, took glibenclamide yesterday
  - a. Metformin 850 mg + glibenclamide 2.5 mg  $\rightarrow$  metformin 1700 mg
  - b. Metformin 850 mg + glibenclamide 5 mg  $\rightarrow$  metformin 1700 mg + glibenclamide 2.5 mg
  - c. Metformin 850 mg + glibenclamide 10 mg  $\rightarrow$  metformin 1700 mg + glibenclamide 5 mg
  - d. Metformin 1700 mg + glibenclamide 2.5 mg  $\rightarrow$  metformin 1700 mg
  - e. Metformin 1700 mg + glibenclamide 5 mg  $\rightarrow$  metformin 1700 mg + glibenclamide 2.5 mg
  - f. Metformin 1700 mg + glibenclamide 10 mg  $\rightarrow$  metformin 1700 mg + glibenclamide 5 mg
  - g. Metformin 2550 mg + glibenclamide 2.5 mg  $\rightarrow$  metformin 2550 mg
  - h. Metformin 2550 mg + glibenclamide 5 mg  $\rightarrow$  metformin 2550 mg + glibenclamide 2.5 mg
  - i. Metformin 2550 mg + glibenclamide 10 mg  $\rightarrow$  metformin 2550 mg + glibenclamide 5 mg
- 23. Metformin and glibenclamide, hypoglycemia symptoms, adherent, did not take glibenclamide yesterday  $\rightarrow$  same as #22
- 24. Metformin and glibenclamide, hypoglycemia symptoms, nonadherent, did not take glibenclamide yesterday → same as #22
- 25. Metformin and glibenclamide, problems with metformin, hypoglycemia symptoms, adherent, took glibenclamide yesterday
  - a. Agrees to take metformin
    - i. Metformin 850 mg + glibenclamide 2.5 mg → metformin 850 mg
    - ii. Metformin 850 mg + glibenclamide 5 mg  $\rightarrow$  metformin 850 mg + glibenclamide 2.5 mg
    - iii. Metformin 850 mg + glibenclamide 10 mg  $\rightarrow$  metformin 850 mg + glibenclamide 5 mg
  - b. Refuses to take metformin
    - i. Metformin 850 mg + glibenclamide 2.5 mg  $\rightarrow$  need MD consult to determine meds
    - ii. Metformin 850 mg + glibenclamide 5 mg  $\rightarrow$  glibenclamide 2.5 mg
    - iii. Metformin 850 mg + glibenclamide 10 mg  $\rightarrow$  glibenclamide 5 mg

#### [name]

- c. Metformin 1700 mg + glibenclamide 2.5 mg  $\rightarrow$  metformin 850 mg
- d. Metformin 1700 mg + glibenclamide 5 mg  $\rightarrow$  metformin 850 mg + glibenclamide 2.5 mg
- e. Metformin 1700 mg + glibenclamide 10 mg  $\rightarrow$  metformin 850 mg + glibenclamide 5 mg
- f. Metformin 2550 mg + glibenclamide 2.5 mg → metformin 1700 mg
- g. Metformin 2550 mg + glibenclamide 5 mg  $\rightarrow$  metformin 1700 mg + glibenclamide 2.5 mg
- h. Metformin 2550 mg + glibenclamide 10 mg  $\rightarrow$  metformin 1700 mg + glibenclamide 5 mg
- 26. Metformin and glibenclamide, problems with metformin, hypoglycemia symptoms, nonadherent, took glibenclamide yesterday → same as #25
- 27. Metformin and glibenclamide, problems with metformin, hypoglycemia symptoms, adherent, did not take glibenclamide yesterday → same as #25
- 28. Metformin and glibenclamide, problems with metformin, hypoglycemia or hypoglycemia symptoms, nonadherent, did not take glibenclamide yesterday → same as #25

#### 400≤FBG<HI

- Urgent MD visit recommended in all cases
  - Patient willing to go
    - Dispense 5 days' worth of meds as a bridge based on 180(200)≤FBG<400 recommendations
    - Arrange appointment
  - Patient unwilling to go
    - Dispense medications based on 180(200)≤FBG<400 recommendations
    - Follow up in 1-3 days

